(T-CAP), a technology-based intervention **development** and **feasibility** R21 study to examine the impact of integrating clinical telehealth services within an existing Illinois (IL) police Opioid Diversion Program (ODP). The study includes three key components: 1) Development and testing of the proposed multidisciplinary telehealth intervention integrated within a state-supported police diversion program; 2) use of telehealth technology to provide ODP participants with access to clinically qualified staff (referred to as the Coach); and 3) expanding and strengthening the available service infrastructure including pain management alternatives to the use of potentially addictive medications and by having the Coach reach out to new and underutilized providers in local communities (e.g., underutilized physicians and other medical providers such as certified nurse practitioners). Modifications target use of virtual consenting and utilizing FedEx mail to issue study cell phones to participants, replacing in-person meetings with the T-CAP research assistant. No modifications have been made to the T-CAP telehealth intervention and **no in-person interactions will occur as a part of this study**. 10.28.2022 modification will include the removal of the randomization procedure; specifically, no one will be assigned to what was previously referred to as the "Treatment as Usual" condition. All participants will receive the T-CAP telehealth intervention.

The specific aims for the proposed research are as follows: (Aim 1) Demonstrate intervention feasibility by measuring study participant receptivity and utilization of the telehealth approach, and (Aim 2) Evaluate the proposed T-CAP measures to assess their performance in gauging the impact of telehealth on initiation of in-person Substance Use (SU) treatment, short-term retention in referred SU treatment, and access to other appropriate treatment services.

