11. Subject Population: Describe the characteristics of the participant population including the inclusion and exclusion criteria and the number of participants you plan to recruit:

A total of 40 clients admitted to the Opioid Diversion Program (ODP) will be enrolled for the T-CAP study and all will receive the T-CAP intervention. Since the sample will be drawn from the existing ODP, sociodemographic characteristics are expected to be similar to census demographics for the corresponding communities, with approximately 59% male, 88% white, and average age of 32. In addition, we expect approximately 40% will need mental health services as part of their treatment and 60% will need services for medical problems. The ODP screens out individuals who have a criminal record of violent offenses. While all current ODP clients have a recent history (within the past 12 months) of opioid use or other substance use, we will confirm this during the RA's administration of the TCU Drug Screen 5 and TCU Drug Screen 5—Opioid Supplement. If this process reveals that the individual does not have a recent history of opioid or substance use, they will be offered the opportunity to remain in the study but excluded from the primary analyses. Furthermore, individuals who are not willing to consent to granting research staff permission to access their police and treatment services records, and individuals who do not understand the informed consent (see appendix for the Informed Consent Comprehension Questions), will be excluded from the study. Individuals must demonstrate the ability to speak and understand English and be at least 18 years old to participate in this study. At the Informed Consent meeting, the RA will determine that these criteria are met.

[figure not shown]
12. Recruitment Procedure: Describe your recruitment strategies including how the potential participants will be approached and precautions that will be taken to minimize the possibility of undue influence or coercion. Include copies of the recruitment letters, leaflets, etc. in your submission.

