Aim 2: Evaluate the proposed T-CAP measures to assess their performance in gauging the impact of telehealth on initiation of in-person Substance Use (SU) treatment, short-term retention in referred SU treatment, and access to other appropriate treatment services (e.g., MAT). Our multidimensional approach includes data from self-report attendance and treatment engagement, self-report drug use, Coaches' advocate records on number of completed assertive referrals, and agency records from police and BH providers (including intake and during-program UA test results). In order to examine groups differences for intervention completers (C) vs non-completers (NC) (i.e., individuals who do not complete the 7 coaching video calls), group differences using t-tests and chi-square tests and we will estimate effect sizes needed for determining a sample size for a future R01 proposal. To assess potential assignment bias, we will test to see if there are baseline differences in demographics: participant race, gender, age and other demographic characteristics, as well as baseline measures of opioid use frequency and amount will be examined using chi-square and t-tests. Effect sizes will be computed for group differences on multiple outcomes (treatment initiation, retention, referrals to expanded SU service options, missed appointments). Service attendance records will be corroborated monthly with service provider records. Examinations of referrals to MAT and alternative pain management care between the C and NC groups, utilizing agency records data and the Coach tracking, will be conducted using a z-score to test differences in proportions of referral types. This will be calculated for all assertive referrals (resulting in scheduled appointments) collectively for a participant, as well as for different types of services.

Analyses of Secondary outcomes. We will examine differences between C and NC groups on several secondary outcomes. Analyses will typically involve t-tests, chi-square tests, and correlations. For example, we will use t-tests to assess differences between groups on the 3-month follow-up measures

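### The only comparability check on the self-selected completer and non-completer groups is significance testing in at most 40 people, which cannot show comparability, and the effect sizes are planned unadjusted whatever the tests find

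*Combined protocol and SAP*

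**What the plan says.** The summary at the start of the protocol records that randomisation was removed in the October 2022 modification: "All participants will receive the T-CAP telehealth intervention". Section 11 sets the size: "A total of 40 clients admitted to the Opioid Diversion Program (ODP) will be enrolled for the T-CAP study". People found to have no recent opioid or substance use may stay, but "they will be offered the opportunity to remain in the study but excluded from the primary analyses", so 40 is an upper limit.

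Section 14, Aim 2, forms two groups after the fact. Non-completers are "individuals who do not complete the 7 coaching video calls"; the rest are completers. The expected split is not given. On comparability the section says "To assess potential assignment bias, we will test to see if there are baseline differences in demographics". It lists race, gender, age and other demographics, and adds that "baseline measures of opioid use frequency and amount will be examined using chi-square and t-tests".

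The same section plans effect sizes for the outcomes (initiation, retention, referrals, missed appointments) and says that estimates from this comparison will help size a future R01. For the baseline comparison it gives no effect size, confidence interval, significance level or threshold for a meaningful imbalance. No adjusted analysis is described.

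**The concern.** The label fits a two-arm design, in which a check on assignment has a meaning. Here the groups are formed by what participants do during the 12 weeks, so there is no assignment to check. People who finish seven calls can be expected to differ at entry from people who do not. The useful question is how large the differences are on variables related to outcome. A significance test in about 40 people answers a different question and mostly reflects the small sample.

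A report of no significant baseline differences would carry little information, yet readers may take it as reassurance. The effect sizes would also remain unadjusted, since no step follows the test in either direction. Those effect sizes are intended for planning a larger trial, so an inflated one could lead to a trial that is too small.

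**Working it through.** **Inputs from the documents.** N is at most 40 (section 11). The groups are completers and non-completers, and the tests are t and chi-square (section 14). The expected sample is "approximately 59% male, 88% white, and average age of 32" (section 11).

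**Assumptions, because the documents give no figure.** Two-sided level 0.05 (0.10 also shown); splits from 20:20 to 32:8; imbalance of 0.5 SD in one continuous variable. The plan states no power or detectable difference for this check, so there is no figure of its own to reproduce.

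**Step 1: miss rate for one variable.** The noncentrality parameter is d × √(n1·n2/(n1+n2)), with n1+n2−2 = 38 degrees of freedom and critical value 2.024. The miss rate is 1 − power. At 20:20 the noncentrality is 0.5 × √(400/40) = 1.58.

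| Split | Power at 0.5 SD | Missed, level 0.05 | Missed, level 0.10 | Imbalance needed for 80% power |
|---|---|---|---|---|
| 20:20 | 34% | 66% | 54% | 0.91 SD |
| 28:12 | 29% | 71% | 59% | 0.99 SD |
| 30:10 | 27% | 73% | 62% | 1.05 SD |
| 32:8 | 23% | 77% | 65% | 1.14 SD |

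If exclusions reduce N to 32 (assumed), the miss rate at level 0.05 is 72% (16:16) to 78% (24:8). For a binary variable at 71% versus 46%, roughly half an SD, it is 64% (20:20) to 70% (30:10) with N = 40. By the normal approximation, 80% power at 0.5 SD needs about 63 per group.

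**Step 2: race.** On the plan's 88% white, the expected number of non-white participants is 0.12 × 40 = 4.8. At 20:20 that is 2.4 per group, too few for a reliable chi-square test.

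**Step 3: where the miss rate stops being high.** It falls below 50% once the imbalance exceeds about 0.64 SD (20:20) or 0.73 SD (30:10). At 0.8 SD it is 31% and 43%. If five independent variables are each off by 0.5 SD, the chance that none is flagged is 0.662^5 = 13% (20:20) or 0.734^5 = 21% (30:10). If only one of the five is off, none is flagged 0.662 × 0.95^4 = 54% of the time (20:20).

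**Step 4: what an imbalance could do (illustration).** Suppose a covariate is off by 0.5 SD and correlates 0.5 with the outcome; both values are assumed. The bias is about 0.5 × 0.5 = 0.25 SD. If a true 0.50 SD effect then appears as 0.75 SD, the normal-approximation sample size for 80% power, 2 × (1.96 + 0.84)² / d², drops from about 63 to about 28 per group.

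**The case against.** A reader might infer that comparability will be decided by these tests, and that bias will usually be declared absent when it is present. The documents do not support that. Section 14 says only that differences will be tested in order to assess bias. It sets no level, and no sentence treats a non-significant result as balance. Nor does *usually* hold in general: Step 3 shows that larger imbalances are more often caught, and that when several variables are off at least one is often flagged.

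It can also be said that, since nothing follows the test, its power changes no estimate. That is correct on the plan as written. It moves the weight of the point to the missing adjustment and to how little a non-significant result could tell a reader.

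In section 14 under Aim 1, the authors say that trends interest them more than significance when they look at participants with high and low participation. That is close to the same contrast and shows a sensible attitude. But the remark is not repeated for Aim 2, where tests are the only named method.

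Finally, this is a feasibility study that makes no efficacy claim from this contrast. The remedy is limited too: at 28:12 the 95% interval for a standardised difference is roughly ±0.7 SD, and adjustment reaches only measured variables. These points limit the severity but do not remove the gap.

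**Conclusion.** The point holds in a limited form. The plan's only check on comparability is significance testing in at most 40 people, under a label that no longer applies. For any one continuous variable off by 0.5 SD, such a test misses it about 66% to 77% of the time, assuming a two-sided 5% level and splits from 20:20 to 32:8. A non-significant result therefore cannot show comparability. The outcome effect sizes have no planned adjustment, whatever the tests show. The imbalance, level and split are assumptions, and the 0.25 SD bias is an illustration rather than an estimate. This is worth correcting before analysis because the remedy is cheap, but it does not undermine the feasibility aim.

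**What to change.** In section 14, Aim 2:

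1. Delete the reference to assignment bias and describe completers and non-completers as self-selected groups.
2. Replace the baseline tests with a standardised difference and 95% confidence interval for each listed variable.
3. Report every completer versus non-completer effect size both unadjusted and adjusted, regardless of any baseline result. Use a short list fixed in advance: baseline substance-use frequency, age, and the outpatient or residential series. For CEST outcomes, add the baseline value; Study Procedures says the follow-up battery repeats the baseline measures, which implies that one is available.
4. State that adjustment does not remove self-selection through unmeasured factors.

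The cost is a change of wording and a small amount of analysis, with no new data collection. Adjusted estimates lose some precision. For binary outcomes with few non-completers they may be unstable, so use fewer covariates or a penalised model there.

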Successful completion of the aims is expected to: 1) establish preliminary evidence to support the efficacy of telehealth technology to augment SU treatment for individuals with misused any form of opioids, alcohol, or other substances, 2) provide support for integrating a clinical role in police opioid diversion practices recently expanded to include individuals at high risk for opioid and/or other substance misuse, 3) provide an empirical examination of how clinical advocacy and telehealth can support individuals with substance use treatment, and 4) demonstrate the value in building relationships with stakeholders to leverage community resources for addressing the SU treatment needs. Findings from this research will inform a future R01 application that will include a multi-site randomized clinical trial, testing the T-CAP intervention and taking a closer look at characteristics of individuals (e.g., sex and race/ethnicity) in relation to intervention response and outcomes in an effort to understand how best to tailor the T-CAP intervention for specific subgroups.

10. Background: Describe the theory or data supporting the objectives of the study and include a bibliography of key references as applicable.

This project focuses on opioid use and other serious substance and alcohol use placing individuals at high risk for behavioral and healthcare problems. The opioid crisis has reached epidemic proportions (Gomes et al., 2018), driven by abuse of prescription opioids and illicit use of fentanyl (CBHSQ, 2017; Moore et al., 2017; O'Donnell et al., 2017; Rudd et al., 2016). The overdose deaths attributed to these drugs (CDC, 2017; Warner et al., 2016) is impacting nearly every community.

In response, IL and several other states are experimenting with diversion program models (Addiction Policy Forum, 2017; Schiff et al., 2017) to intervene with people at the point of contact with police. These individuals are diverted into services designed to prevent further drug use and related problems (Schiff et al., 2017; Reichert et al., 2017). Diversion programs, such as established mental health courts, have been in operation for over two decades and have a proven record of efficacy

(Cosden et al., 2005; Ramirez et al., 2015). Similarly, the IL Police ODP offers an unprecedented opportunity to address the current widespread opioid use, evidenced by an increase of more than 70% from 2013 and a 32% increase from 2015 to 2016 (IDHA, 2017).

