of treatment motivation and psychosocial function from the TCU Client Evaluation of Self and Treatment (TCU CEST), a widely used form listed on the IBR web page. Validation of recent (last few days) self-reported opioid use will be compared with drug testing outcomes at each assessment time point using McNemar's test for change of state, as well as computing sensitivity and specificity statistics and the kappa statistic as a measure of agreement. We will compare self-report, as well as urinalysis (UA) results from agency drug screens between the two groups.

15. Potential Risks and Precautions to Reduce Risk: Indicate any physical, psychological, social, or privacy risk which the subject may incur. Risk(s) must be specified. Also describe what measures have been or will be taken to prevent and minimize each of the risks identified. If any deception is to be used, describe it in detail and the plans for debriefing.

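### Opioid use is the only substance-use measure in the baseline check of completers against non-completers and in the self-report validation, although users of only alcohol or other drugs are eligible and analysed

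*Combined protocol and SAP*

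**What the plan says.** The population is broad. The text before item 10 hopes to support telehealth for "individuals with misused any form of opioids, alcohol, or other substances", and item 10 opens with "This project focuses on opioid use and other serious substance and alcohol use". Item 11 states that "A total of 40 clients admitted to the Opioid Diversion Program (ODP) will be enrolled", all receiving the intervention, and describes current clients as having a "recent history (within the past 12 months) of opioid use or other substance use". The TCU Drug Screen 5 and its Opioid Supplement are used to confirm this. A participant leaves the primary analyses only if the screen shows that he or she "does not have a recent history of opioid or substance use". Someone who uses alcohol or stimulants but no opioids therefore stays in.

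The analysis is narrower. Item 14, Aim 2 compares those who complete the seven video calls with those who do not, and plans baseline tests for what it calls assignment bias. The background variables are listed as "participant race, gender, age and other demographic characteristics". The one addition concerning substance use reads "as well as baseline measures of opioid use frequency and amount will be examined using chi-square and t-tests". No alcohol or other-drug measure is named.

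Under the secondary outcomes, "Validation of recent (last few days) self-reported opioid use" is set against drug-test outcomes using McNemar's test, sensitivity, specificity and kappa. The plan does not restrict this to opioid users and does not say which drug a positive test refers to. The provider form, under Agency Records in Study Procedures, asks only for the month's drug test results.

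**The concern.** Randomization was removed in the October 2022 modification, so completers and non-completers are self-selected groups. Severity of substance use could affect both finishing seven calls and staying in treatment. The baseline comparison is the check that Aim 2 names for such bias, and the effect sizes from these groups are meant to set the sample size of the future trial. If the only severity variable is zero for every non-opioid user, the check may look balanced while the groups differ in alcohol or stimulant severity.

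The validation has a related weakness. Non-opioid users enter the two-by-two table with a self-report of no opioid use. What they do to the agreement statistics depends on how the test is scored, which the plan leaves open. The published statistics would then depend on case mix and on an unstated coding choice as well as on how truthfully people report.

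**Working it through.** The plan gives no power calculation and no target kappa, sensitivity or specificity, so there is no figure to reproduce.

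**Baseline check.** Let s be the share of non-opioid users in a group and m the mean opioid frequency among its opioid users. The group mean is (1 − s) × m. The use frequency of the non-opioid users does not appear in it, so any difference between groups in that frequency is invisible. The mean also mixes s with m, so equal means do not imply equal case mix or equal opioid severity. This holds for any s above zero and needs no assumption about drug tests.

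**Validation.** Notation: a = self-report positive, test positive; b = positive, negative; c = negative, positive; d = negative, negative.

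- Agreement = (a + d)/n
- Sensitivity = a/(a + c)
- Specificity = d/(b + d)
- Kappa = 2(ad − bc)/[(a + b)(b + d) + (a + c)(c + d)]
- McNemar's exact test uses b and c only

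From the documents: N = 40. Assumed, because the documents are silent: 20 of the 40 are non-opioid users, all report no opioid use, and the 20 opioid users have cells (6, 2, 4, 8). Under any-drug scoring, the opioid users' cells are assumed unchanged and half of the other 20 test positive.

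| Table (a, b, c, d) | Agreement | Kappa | Sensitivity | Specificity | McNemar p |
|---|---|---|---|---|---|
| Opioid users only (6, 2, 4, 8) | 14/20 = 0.70 | 80/200 = 0.40 | 6/10 = 0.60 | 8/10 = 0.80 | 44/64 = 0.69 |
| All 40, opioid-scored, 20 added to d (6, 2, 4, 28) | 34/40 = 0.85 | 320/560 = 0.57 | 6/10 = 0.60 | 28/30 = 0.93 | 0.69 |
| All 40, any-drug, 10 added to c and 10 to d (6, 2, 14, 18) | 24/40 = 0.60 | 160/800 = 0.20 | 6/20 = 0.30 | 18/20 = 0.90 | 274/65536 = 0.004 |

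With opioid scoring, the added pairs leave a, b and c alone, so sensitivity and McNemar's test cannot move. Kappa rises with d towards 2a/(2a + b + c) = 12/18 = 0.67.

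**Range.** With N held at 40, the non-opioid share was varied from 0% to 75% under assumed values among opioid users. Opioid scoring:

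| Test-positive rate, sensitivity, specificity | Kappa, 0% to 75% | Agreement | Specificity |
|---|---|---|---|
| 40%, 0.7, 0.9 | 0.615 to 0.732 | 82.0% to 95.5% | 0.90 to 0.98 |
| 50%, 0.7, 0.8 | 0.500 to 0.701 | 75.0% to 93.8% | 0.80 to 0.97 |
| 30%, 0.6, 0.9 | 0.525 to 0.629 | 81.0% to 95.2% | 0.90 to 0.98 |

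Any-drug scoring was run for the first two rows. At a 75% share with half of the non-opioid users positive, kappa falls to 0.124 and 0.125, and sensitivity to 0.147 and 0.175. With 20% positive, kappa falls to 0.333 and 0.347. The one case without a fall is the second row at a 25% share and 20% positive, where kappa is flat (0.501 against 0.500).

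**The case against.** A fair defence has five parts.

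First, the baseline check is not blind in general: it covers race, gender, age and other demographics. Aim 1 also looks at who participates more or less, Aim 2 lists self-reported drug use and intake urinalysis as data, and the closing group comparison of self-report and urinalysis is not confined to opioids. This stands against any claim that comparability rests on opioid measures alone. It does not fill the gap: no non-opioid severity variable is named for the baseline check, and the closing comparison is of outcomes.

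Second, a reader might infer that non-opioid users simply inflate agreement. The documents do not support that, because no analyte is stated and any-drug scoring mostly pushes kappa the other way.

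Third, a reader might treat a non-opioid user as a certain double negative. Nothing in the documents says so, and detecting undisclosed opioid use is a reason to validate at all.

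Fourth, agreement in the whole sample is a legitimate quantity for a study of how measures perform in its own population, and zero is the correct opioid value for a non-user. That stands, so the full-sample analysis should not be replaced. Restricting it to those who report opioid use would select on the measure being validated. If 2 of the 4 false negatives in (6, 2, 4, 8) also denied use at baseline, the restricted table is (6, 2, 2, 8). Sensitivity then rises from 60% to 6/8 = 75%, and kappa from 0.40 to 88/160 = 0.55.

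Fifth, one more low-powered test cannot remove confounding between self-selected groups. True, but the planned check should at least describe severity for everyone analysed.

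**Conclusion.** The mismatch is real and can be read directly from the text. The baseline check cannot show imbalance in severity among participants who use only alcohol or other drugs; this requires only that some enrol, which items 10 and 11 allow. It bears on the interpretation of Aim 2 and on the effect sizes carried to the next trial.

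For the validation, the supportable conclusion is distortion whose direction depends on scoring. An opioid-scored test raises agreement, specificity and kappa and leaves sensitivity and McNemar's test alone. An any-drug result mostly lowers kappa and sensitivity. The stronger reading, that agreement is inflated outright, would require an opioid-specific test that the plan does not state. The figures of 0.40, 0.57 and 0.20 for kappa illustrate direction only. They rest on assumed cells and an assumed half-and-half case mix, and the actual size cannot be determined from the documents.

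**What to change.** In the Aim 2 baseline check, also compare completers and non-completers on primary substance (opioid, alcohol, other) and on use or severity of that substance. Sources are the drug screen already given or the primary diagnosis on the provider form. The screen's items are not visible in the documents, so the sponsor should first confirm which of them give frequency by substance. Show opioid frequency and amount among opioid users as well as overall.

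In the validation, state the analyte and match it to the self-report: an opioid-positive test against self-reported opioid use. Report other substances separately where provider results allow. Keep the full-sample opioid validation as planned, and show an opioid-user subgroup alongside it, not in its place. Identify that subgroup by self-report, diagnosis or any opioid-positive test, so that membership does not depend on self-report alone.

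The cost is a few more descriptive comparisons and small subgroups at N = 40. For opioids this is mainly a change of analysis wording. Whether other substances can be validated depends on how providers report their tests, which should be checked before it is promised.
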